### **13.2.3. Sample Size Sensitivity**

#### **13.2.3.1. Clinically Meaningful Effect Sizes**

Minimally relevant effect sizes have not been fully determined in IIH given it is a rare disease with relatively few previous trials.

The ICP diagnostic threshold in IIH is 25 cm CSF [Mollan, 2018]. However, it is not necessary to reduce ICP <25 cm CSF to achieve remission from signs and symptoms of IIH in all patients [Sinclair, 2010]. The clinical importance of a particular change in ICP

Study Number: INVEX-CLIN-IIH-301 Protocol	Compound No.: Presendin
	Version: 3.0

will vary depending on the starting ICP and the impact this pressure has on vision and headache. Changes in ICP of 5 cm CSF are generally considered meaningful when treating IIH patients. For example, in a clinical study evaluating the benefits of weight loss in IIH patients, a 16.5% (6.2 cm CSF) reduction in ICP resulted in a statistically significant improvement in headache and vision measures as well as quality of life [Sinclair, 2010]. In the IIH Treatment trial (n=165), a study evaluating the drug treatment acetazolamide against placebo, a reduction of -5.9 cm CSF was seen in association with significant improvement in PMD, OCT measures of papilloedema and quality of life measures [Wall, 2014].

The minimally clinically important change in the perimetric mean deviation adopted into clinical practice was established by the Neuro-Ophthalmology Research Disease Investigator Consortium (NORDIC) group and the IIH Treatment Trial (IIHTT). The investigators found a 0.71dB difference in the PMD between the two trial arms (comparing acetazolamide with placebo) that was clinically meaningful. The change of 0.71dB was interpreted as clinically meaningful as this was accompanied by significant changes in LP opening pressure, papilloedema (measured by OCT), general quality of life and visual related quality of life [Wall, 2014, Bruce, 2016].

The clinically meaningful effect size for MHD reflects that for a phenotypically similar headache, chronic migraine. Recent randomised trials in patients with chronic migraine [Tepper, 2017; Silberstein, 2017], episodic migraine [Goadsby, 2017], or both [Camporeale, 2018] have shown in post-baseline months 1–3, odds of migraine relative to baseline of 0.5–0.8 with placebo and 0.5–0.3 with experimental drugs. Decreases in MHD relative to baseline grew in time, and placebo responses were stronger in chronic migraine than episodic migraine. In the three placebo-controlled, blinded trials, these equated to odds-ratios of migraine compared with placebo of 0.8–0.6, or absolute differences of 1.5–2.5 MHD [Sinclair, 2010; Tepper 2017; Silberstein, 2017; Goadsby, 2017].

#### **13.2.4. Trial Stopping Criteria**

There are no trial-specific stopping rules.

#### **13.3. Data Analysis Considerations**

Study Number: INVEX-CLIN-IIH-301 Protocol	Compound No.: Presendin
	Version: 3.0

### 13.3.1. Estimands

We have specified intercurrent events that are material to the measurement of our primary and secondary outcomes, and unbiased estimation of treatment effects attributable to Presendin.

ICP-lowering medication include: acetazolamide, topiramate, diuretics, glucocorticoids (oral dexamethasone and oral prednisolone). Headache-preventative medications include: amitriptyline, topiramate, nortriptyline, beta blockers, candesartan, sodium valproate, pizotifen, botox, CGRP-therapy.

#### 13.3.1.1. Outcome: Intracranial pressure (ICP)

##### 13.3.1.1.1. Intercurrent event: ICP-lowering medications

All patients are expected to have elevated ICP because it is a defining characteristic of the disease. ICP is a physiological variable that is unlikely to show spontaneous improvement without treatment. For these reasons, we expect ICP-lowering medication use to be greater in the placebo arm. If a patient takes medication that is intended to reduce their ICP, it is logical to expect that their ICP will be reduced. Outcomes from patients that take ICP-lowering medications will confound the estimation of the causal treatment effect of Presendin. We have no data to estimate the length of effects of ICP-lowering medications. For these reasons, we propose to remove 24-week ICP outcomes from all patients that have used ICP-lowering medications and replace these observations with arm-specific imputations. This will allow estimation of the treatment effect that is purely and causally attributable to Presendin. Patients will consent at enrolment to forgo the use of ICP-lowering medications and be informed that taking ICP-lowering medications during the trial would constitute rescue therapy and a treatment failure and be a protocol deviation.

##### 13.3.1.1.2. Intercurrent event: Off-protocol lumbar punctures

Lumbar punctures are commonly conducted to reduce intracranial pressure [Weisberg, 1977; Johnston, 1981; De Simone, 2005]. In some centres, they are given routinely although this has now been advised against in the International IIH Guidelines (Soler, 1998; Mollan, 2018). As such, they remain a material therapeutic option. LP is expected to reduce ICP mean opening pressure 32 (28-37) cm CSF to 19 (17-21) cm CSF post LP [Yiangou, 2019]. Beneficial effects dissipate with time and whilst there has been no longitudinal assessment to quantify change in ICP after an LP, it is expected that effects in the majority of change would have dissipated completely within two months [Yiangou, 2019]. Outcomes from patients that have undergone off-protocol LPs will confound the estimation of the causal treatment effect of Presendin. For these reasons, we propose to remove 24-week ICP outcomes from all patients that have had an off-protocol LP within

Study Number: INVEX-CLIN-IIH-301 Protocol	Compound No.: Presendin
	Version: 3.0

two months of the protocol-scheduled 24-week LP and replace these observations with arm-specific imputations. Where patients require off-protocol LP this would be a protocol deviation.

### **13.3.1.1.3. Inter-current event: Dramatic weight-loss**

Research has shown that weight loss in IIH is associated with reductions in IIH symptoms, including decreases in ICP [Sinclair, 2010]. Sudden dramatic weight loss, e.g. arising from a surgical procedure will likely yield material changes to IIH symptoms. This will confound the estimation of the causal treatment effect of Presendin. For these reasons, we propose to remove 24-week ICP outcomes from all patients that experience weight loss exceeding 10% of baseline weight after a surgical weight-loss procedure and replace with arm-specific imputations. Patients will be ineligible for the trial if they have had a surgical weight-loss procedure within 3 months of randomisation or fail to confirm that they do not intend to undertake such a procedure during the trial. They will also be informed at enrolment that undergoing a surgical weight-loss procedure would be a protocol deviation.

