This trial will investigate an alternative therapeutic option for lowering ICP and thereby reducing papilloedema and consequently reducing the risk of visual loss. By reducing ICP it would also aim to improve headache, improving overall patient quality of life in IIH [Mollan 2021a].

Study Number: INVEX-CLIN-IIH-301 Protocol	Compound No.: Presendin
	Version: 3.0

Gut neuropeptides are increasingly being recognised for their role in the central nervous system (CNS). A principal gut neuropeptide is glucagon like peptide-1 (GLP-1), which is known to stimulate insulin release, proliferation of pancreatic beta cells and control of glucose regulation in diabetes [Campbell, 2013]. Exenatide is a GLP-1 receptor agonist. It has also been shown to have some actions in the CNS; GLP-1 is involved in regulating satiety and weight through signalling at the hypothalamus [Astrup, 2009]. There is also evidence that GLP-1 may have a role in fluid secretion. In the renal proximal tubule GLP-1 acts to reduce sodium resorption to promote diuresis [Gutzwiller, 2004; Websky, 2014]. The choroid plexus is the fluid secreting structure within the brain producing the majority of CSF. The structure of the choroid plexus epithelial cells is analogous to an inverted renal proximal tubule with a similar mechanism of secretion and hence GLP-1 receptor agonists may also reduce CSF secretion in the brain, leading to a decrease in ICP in patients with IIH.

Exenatide as well as other GLP-1 receptor agonists can lead to weight loss. In diabetic patients, weight loss of 2.8 - 4.4 kg has been reported over 6 months [Di Dalmazi 2020; Pujante 2012]. Whilst in non-diabetic overweight and obese patients exenatide caused sufficient weight loss between 2.0 – 5.1 kg [Moreno 2012]. In overweight and obese patients with polycystic ovarian syndrome exenatide led to 2kg more weight loss compared to placebo in over 12 weeks [Liu 2017]. Weight loss with exenatide therapy is increased in the setting of calorie restriction [Rosenstock 2010]. Weight loss is a desirable effect of exenatide as weight loss is therapeutic in IIH. Changes in body weight will be monitored during the trial and the impact on outcomes measures evaluated.

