#### **13.3.1.2.3. Intercurrent event: Dramatic weight-loss**

Research has shown that weight loss in IIH is associated with reductions in IIH symptoms, including improvements in visual fields [Sinclair, 2010]. Sudden dramatic weight loss, e.g. arising from a surgical procedure will likely yield material changes to IIH symptoms. This will confound the estimation of the causal treatment effect of Presendin. For these reasons, we propose to remove PMD outcomes of patients that experience weight loss exceeding 10% of baseline weight after a surgical weight-loss procedure from the date of procedure. These outcomes will be replaced with patient-within-arm imputations generated by a method suitable for longitudinal data imputation.

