**13.3.1.5. Primary Estimand (Hypothetical assuming no concurrent procedures, irrespective of adherence to treatment)**

The primary estimand is defined as the following for the primary endpoint:

- Treatment difference in ICP measurement between Presendin and placebo at Week 24 for all patients who are randomised and start treatment, regardless of adherence to randomised treatment, where patients did not have medications or procedures likely to materially affect ICP.

The primary estimand for the initial secondary endpoint will be handled similarly to the primary endpoint using the “Hypothetical” approach. The initial secondary endpoint is defined as:

- Treatment difference in PMD between Presendin and placebo over 24-weeks for all patients who are randomised and start treatment, regardless of adherence to randomised treatment, where patients did not have medications or procedures likely to materially affect PMD.

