**13.3.2. Analysis Populations**

The following analysis populations are planned for this trial:

Study Number: INVEX-CLIN-IIH-301 Protocol	Compound No.: Presendin
	Version: 3.0

- **Safety Population:** The Safety population includes all patients randomised to treatment who receive at least one dose of trial medication. This will be the population used for all safety analyses unless otherwise specified.
- **Intent-To-Treat Population (ITT):** The ITT population includes all patients randomised to treatment. This will be the main population for all efficacy analyses unless otherwise specified.
- **Per Protocol (PP):** The PP population includes all patients randomised to treatment without important non-evaluable protocol deviations. Only protocol deviations with the potential to affect the trial results significantly, or to invalidate the interpretation of the data obtained, will lead to exclusion of patients from the PP population. Protocol deviations to be considered will include (but will not be limited to):
  - Failure to meet inclusion/exclusion criteria
  - Wrong treatment or incorrect volume of drug administration
  - Prohibited concomitant medications
  - Compliance of less than 75% or >125% with trial drug administration
  - Use of rescue procedures, including, off-protocol LPs, LP shunts or bariatric surgery

Assignment of patients to populations will be confirmed at a blinded data review meeting to be held before the trial database is locked.

If a patient is randomised incorrectly or is administered the incorrect trial medication, analyses of the ITT will be based on the assigned treatment, whereas all other analyses will be based on the actual treatment received.

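### The weight-loss-surgery rule keeps outcomes from operated patients who lose 10% or less, which does not fit the hypothetical estimand; the likely bias is small and towards no difference

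*Protocol*

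**What the plan says.** All references are to Protocol v3.0. The body of v4.0 is not available, so whether the rule still stands there cannot be checked.

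- **Estimand (13.3.1.5).** The primary estimand is hypothetical: the Week 24 difference in ICP "where patients did not have medications or procedures likely to materially affect ICP". No weight threshold is attached.
- **Surgery rule for ICP (13.3.1.1.3).** The plan will "remove 24-week ICP outcomes from all patients that experience weight loss exceeding 10% of baseline weight after a surgical weight-loss procedure" and replace them with arm-specific imputations. The reason given is that "weight loss in IIH is associated with reductions in IIH symptoms, including decreases in ICP".
- **Surgery rule for PMD (13.3.1.2.3).** Outcomes are removed for patients with "weight loss exceeding 10% of baseline weight after a surgical weight-loss procedure from the date of procedure". OCT (13.3.1.3.3) and headache days (13.3.1.4.3) follow the same pattern.
- **Medication rule (13.3.1.1.1).** The plan will "remove 24-week ICP outcomes from all patients that have used ICP-lowering medications". Use alone is the trigger.
- **Off-protocol LP rule (13.3.1.1.2).** The trigger is an LP within two months of the scheduled one: an event and its timing, not the response to it.
- **Drug and weight (1.1).** "Exenatide as well as other GLP-1 receptor agonists can lead to weight loss", with 2.0–5.1 kg quoted for non-diabetic overweight and obese patients. The protocol adds: "Weight loss is a desirable effect of exenatide as weight loss is therapeutic in IIH".

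**The concern.** Removal needs two things: the procedure, and more than 10% weight loss afterwards. An operated patient who loses 9% stays in the main ITT analysis with an ICP that the operation may have lowered, although the estimand asks for the value without such a procedure.

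The second condition is a response observed after randomisation, and one that the protocol expects the drug to influence. If drug-induced loss counts towards the 10%, the same operation crosses the cut more easily on Presendin. Operated placebo patients would then be kept more often, the placebo mean would be pulled down further, and the estimated benefit would shrink. For PMD, OCT and headache, whether an early post-operative value is kept also depends on weight lost later.

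**Working it through.** **1. The plan's own power figure.** Inputs from 13.2.1.1: difference 5 cm CSF, Week 24 SDs 9.4 (control) and 10.4 (Presendin), two-sided 5%, 60 or 72 final LPs per arm.

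- Pooled SD = √((9.4² + 10.4²)/2) = 9.91.
- Baseline adjustment multiplies the SD by √(1 − r²). The protocol does not state r.
- r = 0 gives 78.9% (60 per arm) and 85.7% (72 per arm), below the stated values of about 85% and 91%.
- r = 0.40 gives SD 9.09, z = 5/(9.09 × √(2/60)) = 3.01, power Φ(3.01 − 1.96) = 85.4%; with 72 per arm, 91.0%. Both match the plan.

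**2. Share of operated patients kept.** Suppose surgical loss by Week 24 is normal with mean m and SD s (in %), and the drug adds d = 100 × kg/body weight. Then

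P(kept) = Φ((10 − d − m)/s).

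The drug effect of 2.0–5.1 kg is from section 1.1. Body weight, m and s are assumptions, because the protocol gives none of them.

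| Assumed surgical loss (100 kg) | Kept, placebo | Kept, Presendin (2.0 kg) | Kept, Presendin (5.1 kg) |
|---|---|---|---|
| mean 10%, SD 6% | 50% | 37% | 20% |
| mean 20%, SD 4% | 0.6% | 0.1% | <0.1% |

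Over means of 8–20%, SDs of 4–8% and body weights of 90–110 kg, placebo retention is always higher, by 0.5 to 51 percentage points. The gap is wide when typical surgical loss lies near the cut and almost vanishes when it lies well above it.

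**3. Bias in the ICP difference.** Further assumptions: true effect −5 cm; equal surgery rates q in both arms; mean 10%, SD 6%, 100 kg, negative losses set to zero; ICP falls 0.62 cm per 1% of surgical loss. The last scales the 6.2 cm in 13.2.3.1 to a 10% loss; that scaling is an assumption. Removed values are taken to be imputed at the mean of the kept values in the same arm.

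Arm shift = 0.62 × (mean surgical loss among kept) × q·P(kept)/(1 − q + q·P(kept)).

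- Placebo: mean loss among kept 5.45%, or 3.38 cm.
- Presendin, 2.0 kg: 4.19%, or 2.60 cm.
- Presendin, 5.1 kg: 2.16%, or 1.34 cm.

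Example with q = 10% and 5.1 kg: placebo 3.38 × 0.050/0.950 = 0.178 cm; Presendin 1.34 × 0.0198/0.9198 = 0.029 cm; net 0.149 cm.

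| Operated | Bias (2.0 kg) | Bias (5.1 kg) |
|---|---|---|
| 2% | 0.015 cm | 0.029 cm |
| 5% | 0.037 cm | 0.073 cm |
| 10% | 0.075 cm | 0.149 cm |

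The estimated difference then runs from −4.99 to −4.85 cm. Simulation with 2 million patients per arm agrees. With no drug effect on weight, the two arms shift equally and the bias is zero. With the procedure alone as trigger, the simulated difference is −5.00 cm.

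**4. Effect on power.** At 60 per arm and r = 0.40, power falls from 85.4% to 85.2% (bias 0.015 cm) or 83.3% (bias 0.149 cm).

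**The case against.** The estimand excludes only procedures that are likely to affect ICP materially. The 10% cut can be read as the sponsor's criterion of materiality, and the LP rule is filtered too, by a time window. This has weight: the mismatch is one of fit, not a flat contradiction. But a time window does not depend on how the patient responded, and the 10% cut does.

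Three stronger readings are tempting, and the documents do not support them.

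- **That Presendin will certainly cause unequal removal.** Section 1.1.3 reports no significant weight loss in either arm of the phase 2 IIH trial (15 randomised, 12 weeks, immediate-release product). The wording can also mean loss occurring after the operation, with baseline weight only as denominator. Drug-induced loss before surgery would then not count, and adding the full 2.0–5.1 kg would be too much.
- **That a few kept patients move the result by up to 0.3 cm.** Three kept placebo patients among 60, each 6.2 cm lower, give 3 × 6.2/60 = 0.31 cm. That ignores kept Presendin patients, and those kept have lost 10% or less. Three such patients at 50% retention would also mean six operated per arm, although intended surgery is an exclusion criterion (5.2.2).
- **That the per-protocol definition contradicts the rule.** Section 13.3.2 lists "Use of rescue procedures, including, off-protocol LPs, LP shunts or bariatric surgery" among deviations to be considered, but only deviations that could significantly affect the results lead to exclusion. It carries its own materiality filter.

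The fix has a real drawback: an ICP measured soon after surgery, before weight has changed, would be imputed in a trial that already allows for up to 50% missing final LPs.

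**Conclusion.** The point holds as a mismatch between rule and estimand: operated patients who lose 10% or less keep values that surgery may have affected, for ICP and for the three longitudinal outcomes. This does not depend on any drug effect on weight.

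The difference between arms is conditional. It needs Presendin to lower weight, the 10% to be read as total loss from baseline, and surgical losses not far above the cut. Under those conditions, with equal surgery rates, the net bias is about 0.015–0.15 cm of the 5 cm target for 2–10% operated. Surgery should be rare, because intended surgery is excluded and undergoing it is a protocol deviation. The direction is towards no difference, so the mechanism works against Presendin and does not favour a false claim of benefit. This is a cheap improvement, not a threat to the trial's conclusion.

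**What to change.** In 13.3.1.1.3, 13.3.1.2.3, 13.3.1.3.3 and 13.3.1.4.3, make the surgical weight-loss procedure itself the intercurrent event. Remove and impute outcomes measured after its date, whatever weight is lost, and delete the condition of more than 10% loss. Weight loss without surgery, including any caused by the drug, stays in the analysis as now. If v4.0 is in force, check its wording first.

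The cost is one phrase in four subsections and a few more imputed values, including some measured soon after surgery before weight has changed.

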### **13.3.1.2. Outcome: Perimetric Mean Deviation (PMD)**

#### **13.3.1.2.1. Intercurrent event: ICP-lowering medications**

All patients are expected to suffer from some visual field loss at enrolment because it is the hallmark feature of the disease [Wall, 2014; Ottridge, 2017; Markey, 2020]. If a patient takes ICP-lowering medication (rescue medication due to treatment failure), it is logical to expect that their ICP will decrease and that papilloedema will reduce as a result, allowing visual fields to improve. As stated, we expect ICP-lowering medication use to be greater in the placebo arm. Outcomes from patients that take these medications will confound the estimation of the causal treatment effect of Presendin. For these reasons, we propose to remove the PMD outcomes following the administration of ICP-lowering medications and replace these observations with imputations generated by a method suitable for longitudinal data imputation. Outcomes recorded at the unscheduled visit when the treatment failure is confirmed (and just prior to starting ICP lowering medication) will be defined as the last analysed visit. This will allow estimation of the treatment effect that is purely and causally attributable to Presendin.

#### **13.3.1.2.2. Intercurrent event: Off-protocol lumbar punctures**

As discussed above, LPs are a material and widespread intervention in the treatment of IIH, given with the intention of reducing intracranial pressure and improving the associated symptoms of the disease, including reducing pressure on the optic nerve and papilloedema, allowing visual fields to improve. Patients that have LPs are expected to experience less pressure on the optic nerve, less papilloedema, and have better chances of

Study Number: INVEX-CLIN-IIH-301 Protocol	Compound No.: Presendin
	Version: 3.0

their visual fields improving. Beneficial effects dissipate with time and whilst there has been no longitudinal assessment to quantify papilloedema after an LP the consensus of clinicians would predict that effects of the LP on papilloedema and therefore visual fields would have dissipated by one month. Outcomes from patients that have undergone off-protocol LPs will confound the estimation of the causal treatment effect of Presendin. PMD outcomes will be recorded repeatedly during the trial. For the reasons stated, we propose to remove PMD outcomes recorded in the 4-weeks following an off-protocol LP, and replace these observations with patient-within-arm imputations generated by a method suitable for longitudinal data imputation.

#### **13.3.1.2.3. Intercurrent event: Dramatic weight-loss**

Research has shown that weight loss in IIH is associated with reductions in IIH symptoms, including improvements in visual fields [Sinclair, 2010]. Sudden dramatic weight loss, e.g. arising from a surgical procedure will likely yield material changes to IIH symptoms. This will confound the estimation of the causal treatment effect of Presendin. For these reasons, we propose to remove PMD outcomes of patients that experience weight loss exceeding 10% of baseline weight after a surgical weight-loss procedure from the date of procedure. These outcomes will be replaced with patient-within-arm imputations generated by a method suitable for longitudinal data imputation.

